Mopati: A Pilot HIV Treatment Partner Intervention in Botswana (R34MH121229)

NCT04796610

Study Protocol and Statistical Analysis Plan

August 12, 2023

STUDY PROTOCOL

Low-cost, scalable interventions are essential to support people living with HIV to adhere to antiretroviral therapy (ART) and remain in care. One such intervention is the use of treatment partners, which are recommended by HIV treatment guidelines worldwide. Specifically, national HIV policies of several countries, including Botswana, recommend that healthcare providers encourage patients initiating ART to identify an individual who can provide support, accompany patients to appointments, and provide medication reminders. Although a large body of work indicates the key role of social support in promoting adherence, research on treatment partners' effectiveness has shown mixed results. Thus, research is needed to determine how support from treatment partners can be better harnessed. We propose to pilot test the effects of the *Mopati* program ("partner" in Setswana, the official language of Botswana), a multi-level intervention that guides healthcare providers and patients about treatment partner selection, and trains treatment partners on provision of effective support. The Specific Aims are: (1) To develop a multi-level treatment partner intervention with input from community and healthcare provider stakeholders in Botswana; and (2) To conduct a pilot test of the feasibility, acceptability, and preliminary effects on viral suppression of a multi-level treatment partner intervention.

Intervention Pilot Test. We will recruit 60 people living with HIV who are not virally suppressed and their 60 treatment partners in 1 matched-clinic pair (30 dyads/clinic) in Gaborone, Botswana. We will obtain updated data on 7 satellite clinics in the Greater Gaborone area, and match satellite clinics on number and type of staffing, number of patients total, and number of unsuppressed patients by calculating Euclidean distances between all possible pairs to determine the best (closest) matches, and then selecting one pair of matched intervention and control clinics. Clinics will be randomly assigned to standard of care or a healthcare provider guidance and treatment partner training intervention. In the randomly selected clinic over a 9-month period, (1) clinic healthcare providers will offer guidance around treatment partners to patients who are unsuppressed, in addition to patients who are initiating treatment (although we will only assess intervention effects among those who are not suppressed); and (2) the clinic will offer monthly, open treatment partner training sessions, and request that treatment partners of unsuppressed patients attend ≥ 2 sessions, one within a month after baseline, and one within 3 months after baseline. Patients and treatment partners will be asked to attend two sessions together, so that they can practice role-plays with each other: one within a month after the baseline interview, and one ~ 3 months later (as a booster session). To better fit with clinic flow and the way in which the sessions would ultimately be disseminated and implemented into clinics, the sessions will be open to all treatment partners (regardless of study enrollment) and run monthly for 9 months (during the length of time that the intervention is tested in the clinic). Each one-hour monthly open treatment partner group training session will consist of the same three components: (1) basic HIV treatment education (e.g., names and descriptions of medications and how they work, why adherence is important, how to manage side effects); (2) introduction to Motivational Interviewing (MI), why well-meaning partners can sometimes be unhelpful, how MI strategies (open questions, reflective listening) can be used to better support patients' motivation, and psychoeducation with examples of different types of treatment partner support activities that may be helpful in addition to adherence reminders; and (3) role-plays between patients and treatment partners of different types of challenging situations,

All patients and treatment partners will be surveyed at baseline and 3-months post-baseline, and patients' viral loads will be extracted from medical records from baseline to 6-months post-baseline. We will obtain viral load suppression rates for the intervention and control clinic at baseline and 12-months post-baseline. We will conduct an implementation process evaluation of acceptability and feasibility in the intervention clinic, using semi-structured interviews with patients and treatment partners about their experiences with attending the sessions, and healthcare providers about their experiences with intervention implementation, and suggestions for improvement.

Patients will eligible if they (1) are 18 years of age or older; (2) are on ART and initiated ART at least 6 months prior (to have sufficient time to confirm viral load); (3) are not virally suppressed (at least two viral loads ≥ 400 cp/ml within prior 12 months at time of enrollment) and do not show viral resistance in the past 6 months. Viral

load and time from ART initiation will be confirmed with clinic records before enrollment. We will recruit 80 patients (20 per clinic; half men and half women) and their 80 treatment partners. Patients will not be eligible if they screen positive for HIV-related dementia (from clinic records) and if they have not been tested for viral resistance as part of standard of care (all patients failing second-line ART and some patients failing first-line ART are undergo resistance testing). A study nurse will pre-screen patient charts and place study fliers in eligible patients' charts to remind providers to mention the study during the appointment. Interested patients will be told that they can meet with an interviewer in a private clinic space before or after the appointment or at another convenient time for an eligibility screening. Participants can be interviewed immediately after the screening or make an appointment for another time by phone or in person.

Treatment partners will be eligible if they (1) are 18 years-old or older and (2) were selected to be the PLWH's treatment partner. Based on our pilot, we expect that some treatment partners will also be HIV-positive, and if so, patients and treatment partners may select each other as their treatment partners. For the purposes of study design, we will consider the first patient recruited to be the patient, and the patients' treatment partner to be the treatment partner (regardless of whether the treatment partner is also a patient). After patient and treatment partner participants in the intervention clinic complete the baseline interview, they will be asked to attend the next treatment partner training session (in the next month after the baseline interview), as well as in three months.

STATISTICAL ANALYSIS PLAN

Consistent with R34 guidelines, our primary purpose is to collect preliminary data on feasibility, acceptability, and outcomes; conducting formal tests of outcomes for a measure of effect size is not justified with limited sample size. Thus, the proposed analyses are meant to be exploratory, to help plan for a full RCT. We do not expect to have sufficient statistical power to adequately examine effects. We will calculate descriptive statistics and conduct bivariate analyses of intervention-control differences in change. We will use logistic regression to examine changes in viral suppression (% suppressed at follow-up, % adherent to at least 95% of doses) among enrolled patients in intervention and control clinics. We will use linear regression to examine changes in other survey outcomes (e.g., dyadic relationship support).

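### Does leaving the scaling of the clinic-matching distance unstated mean the pair is matched on clinic size alone?

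*Combined protocol and SAP*

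**What the plan says.** The Intervention Pilot Test paragraph of the Study Protocol sets out the matching. The candidates are seven clinics: "We will obtain updated data on 7 satellite clinics in the Greater Gaborone area". The variables are given as "match satellite clinics on number and type of staffing, number of patients total, and number of unsuppressed patients". The method is to proceed "by calculating Euclidean distances between all possible pairs to determine the best (closest) matches", "then selecting one pair of matched intervention and control clinics". Allocation follows: "Clinics will be randomly assigned to standard of care or a healthcare provider guidance and treatment partner training intervention". Nothing is said about units, standardisation, weights, or how type of staffing becomes a number.

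The same paragraph describes "60 treatment partners in 1 matched-clinic pair (30 dyads/clinic". The Statistical Analysis Plan treats all outcome analyses as exploratory and states "We do not expect to have sufficient statistical power to adequately examine effects".

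**The concern.** Euclidean distance depends on the units of its inputs. Unsuppressed patients are a subset of all patients, and a clinic normally has far fewer staff than patients. If raw counts go straight into the formula, the variable with the largest spread, total patients, decides which pair is closest. Staffing then has almost no say, although the sponsor chose to match on it.

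This could matter because the design has one pair. Randomising within it decides which clinic is treated but does nothing to make the two alike, so the match is the main design step that does. Clinic staff deliver the provider guidance, so a staffing difference could bear on both delivery and viral suppression.

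**Working it through.** **Figures in the plan.** One pair at 30 dyads per clinic gives 2 × 30 = 60 patients, as stated. Seven clinics give 7 × 6 / 2 = 21 possible pairs. The eligibility text says "We will recruit 80 patients (20 per clinic; half men and half women", and 80 / 20 = 4 clinics. That conflicts with one pair and must be reconciled, but it is a separate matter: the scaling question is the same for one pair or two.

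**Share of the distance on raw counts.** For any variable, the squared differences summed over all pairs of 7 clinics equal 7 × 6 × s², where s² is its sample variance. Each variable's share of the total squared distance is therefore its share of the summed variances. The documents give no clinic values, so everything below rests on assumptions.

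Let total patients have coefficient of variation c, and let the unsuppressed fraction have mean p and coefficient of variation k, independent of size. Leaving staffing aside, the share of total patients is about

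c² / [c² + p²(c² + k² + c²k²)].

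With c = 0.15, p = 0.05 and k = 0.3:

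- c² = 0.0225 and k² = 0.09
- bracketed sum = 0.0225 + 0.09 + 0.002025 = 0.114525
- p² × 0.114525 = 0.0025 × 0.114525 = 0.000286
- share = 0.0225 / 0.022786 = 98.7%

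Simulation of the same case, with staffing included, gives a median of 98.8%.

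**Range.** The simulation covered mean totals of 1,000 and 3,000, c of 0.15 and 0.40, p of 3% to 20%, k of 0.3 and 0.6, and three staff counts of about total/150, total/300 and total/600, with 3,000 sets of 7 clinics per scenario.

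| Quantity | Range over scenarios |
|---|---|
| Share of total patients, raw counts | 65% to 99.9% |
| Share of unsuppressed patients, raw counts | 0.1% to 35% |
| Share of staffing, raw counts | under 0.03% |
| Raw pick is also the pair closest on total patients | 30% to 95% of sets |
| Raw pick is also the standardised pick | 13% to 23% of sets |

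Further runs with totals inside 300 to 4,000, 2% to 20% unsuppressed and 5 to 40 staff kept the staffing share under 0.3%.

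**What raw matching leaves unbalanced.** In those further runs a random pair differs by about 1.2 SD on any one variable. The mean gap in the chosen pair was:

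| Variable | Raw counts | Standardised |
|---|---|---|
| Unsuppressed patients | 0.44 to 0.66 SD | 0.25 to 0.39 SD |
| Staffing, unrelated to clinic size | about 1.2 SD | 0.26 to 0.39 SD |
| Staffing, rising with clinic size (20% noise) | about 0.5 SD | 0.23 to 0.27 SD |

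The 1.2 SD staffing gap is no better than chance, and it arises only if staffing is unrelated to patient volume. Where staffing follows size, matching on size brings much of the staffing balance with it, and the raw and standardised picks agree in 39% to 53% of sets.

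**The case for a change.** The strongest case for acting is that a Euclidean distance without a scale does not determine one pair. The plainest reading of the sentence is raw counts. On that reading staffing is close to ignored in every assumed setting, and in most settings the choice of scale changes which pair is selected. Stating the scale would take one clause.

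The arithmetic stands: had the sponsor used raw counts, staffing would have had almost no influence. Three parts of the case do not stand.

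- The raw-count reading treats silence as a decision. Type of staffing cannot enter a distance until it is coded, so the sentence cannot be carried out literally. It is a summary of a procedure, and standardising first is fully consistent with it.
- Matching on size alone is too strong. At the lower end, the raw and size-only picks coincide in only about 30% of sets, and the number unsuppressed is still partly balanced because it tends to rise with clinic size.
- Stating a scale would not settle the matter by itself. Three staff counts entered separately at equal weight would take three of five shares, while total and unsuppressed counts overlap. Equal weighting is one defensible choice among several.

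**Conclusion.** No change to the plan follows. What remains is an unstated preparatory step that an analyst would ordinarily fill by putting the variables on a common scale. If that was done, nothing is lost. If raw counts were used, the likely cost is a chosen pair that differs on staffing by about 0.5 SD where staffing follows size, and up to about 1.2 SD where it does not, with the unsuppressed gap still cut to about half of what chance would give. These sizes rest entirely on assumed clinic values.

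The consequence is limited by the design. With one clinic per arm, the difference between arms cannot be separated from the difference between clinics however close the match, and better scaling does not alter that. The plan also does not lean on the match alone: it surveys participants at baseline, obtains clinic suppression rates at baseline and 12 months, and compares arms on change. It claims no formal test of effect. For a pilot meant to inform a later trial, the missing detail would not change what can be concluded.

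### The only viral measure reaching beyond enrolled dyads and month 6 is, on its natural reading, a whole-clinic suppression rate, which attenuates any effect in unsuppressed patients

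*Combined protocol and SAP*

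**What the plan says.** Two viral measures appear in the Study Protocol paragraph on surveys and viral loads. For enrolled patients, "patients' viral loads will be extracted from medical records from baseline to 6-months post-baseline". Then, as a separate item: "We will obtain viral load suppression rates for the intervention and control clinic at baseline and 12-months post-baseline". For the second measure the document gives no denominator, no calendar date, no rank among the outcomes and no analysis.

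The Intervention Pilot Test section sets the reach of the intervention. In the intervention clinic, "clinic healthcare providers will offer guidance around treatment partners to patients who are unsuppressed, in addition to patients who are initiating treatment", with the qualification "although we will only assess intervention effects among those who are not suppressed". On the training, "the sessions will be open to all treatment partners (regardless of study enrollment"), and the sessions are "run monthly for 9 months (during the length of time that the intervention is tested in the clinic"). The design there is 60 patients and "60 treatment partners in 1 matched-clinic pair (30 dyads/clinic").

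The Statistical Analysis Plan models suppression by logistic regression "among enrolled patients in intervention and control clinics". It calls all analyses exploratory and expects too little power to examine effects. The clinic rates are not mentioned there.

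**The concern.** The intervention is delivered to a clinic, not only to the enrolled dyads. The enrolled-patient analysis cannot describe what happens to the other unsuppressed patients who are offered guidance, and its viral loads stop at 6 months. Only the clinic rate covers the wider group and the later time.

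Read naturally, though, that rate counts every patient in the clinic, while the stated target of inference is the unsuppressed. An effect in that group is scaled down by its share of the clinic. The one follow-up reading may also come after the sessions have ended, with no reading at their end. A pilot meant to inform a full trial could then carry forward a clinic-level figure that says little about the group of interest.

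**Working it through.** **Inputs from the document.** Intervention length 9 months; clinic readings at baseline and month 12; enrolled-patient viral loads to month 6; one clinic per arm with 30 patients each. No alpha, power, effect size, suppression rate or clinic size is stated, so there is no figure of the plan's own to reproduce.

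**Assumptions.** Share of clinic patients unsuppressed at baseline, u: 2% to 30%. Suppression at follow-up in that group: 30% in control and 50% in intervention, a gain d of 20 points. All other patients: 97% suppressed in both clinics. Clinic size N: 300 to 3,000.

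**Step 1: the denominator.** If the rate were taken only in patients unsuppressed at baseline, the baseline value would be 0% in both clinics. A baseline reading is informative only if suppressed patients are counted too. This supports the whole-clinic reading, although the text does not state it.

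**Step 2: attenuation.** Shift in the clinic rate = u × d. For example, 0.02 × 20 = 0.4 points and 0.30 × 20 = 6.0 points.

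**Step 3: what this does to a comparison.** Power is used only as a yardstick, since the plan claims none. Two-sided 0.05, between-clinic variation ignored (optimistic):

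power = Φ[(d − 1.96·SE₀)/SE₁], with SE₀ = √(2p̄(1−p̄)/n) and SE₁ = √((p₁(1−p₁)+p₂(1−p₂))/n), where d is here the difference p₂ − p₁ between the two rates compared.

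Example at u = 10%, N = 1,000:
- Whole clinic: p₁ = 0.9 × 0.97 + 0.1 × 0.30 = 0.903 and p₂ = 0.923. Both SEs are about 0.0126, so power = Φ[(0.020 − 0.0247)/0.0126] ≈ 0.35.
- Unsuppressed cohort, n = 100: SE₀ = 0.0693 and SE₁ = 0.0678, so power = Φ[(0.20 − 0.1358)/0.0678] ≈ 0.83.

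| u | Shift in clinic rate (points) | Power, whole clinic, N = 1,000 | Power, unsuppressed cohort, N = 1,000 | Power, whole clinic, N = 3,000 |
|---|---|---|---|---|
| 2% | 0.4 | 0.07 | 0.25 | 0.12 |
| 5% | 1.0 | 0.16 | 0.53 | 0.38 |
| 10% | 2.0 | 0.35 | 0.83 | 0.79 |
| 20% | 4.0 | 0.72 | 0.99 | 0.99 |
| 30% | 6.0 | 0.92 | >0.99 | >0.99 |

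With N = 300, whole-clinic power does not exceed 0.45 at any u in the table.

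**Step 4: if only enrolled patients gain.** 30 × 0.20 = 6 more suppressed. The clinic rate moves 6/300 = 2.0, 6/1,000 = 0.6 or 6/3,000 = 0.2 points. The 95% half-width for a difference, 1.96 × √(2 × 0.95 × 0.05/N), is about 3.5, 1.9 and 1.1 points. The cohort is diluted in this case too, but less: with 1,500 patients and u = 10%, 6/150 = 4 points against 6/1,500 = 0.4.

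**Step 5: timing.** If clinic baseline is the start of the intervention, the gap is 12 − 9 = 3 months. If baseline is the date of a patient enrolled m months into the period, the gap is 12 + m − 9 = 3 + m. It is shorter than 3 months only if baseline precedes the start.

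**Step 6: new initiators.** An initiator share of 2% to 10% with no effect multiplies the shift by 0.98 to 0.90. A 5-point benefit in them would add 0.1 to 0.5 points.

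**Step 7: one clinic per arm.** With an assumed between-clinic SD of change of 2 points, the 95% half-width for the difference is 1.96 × 2 × √2 ≈ 5.5 points.

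**The case against.** The strongest reply is that the effect in the target group is handled elsewhere. The planned logistic regression uses enrolled patients, all unsuppressed at entry, which agrees with the statement on where effects are assessed. The clinic rates carry no test, no decision and no power claim. That stands, and it limits the seriousness of the point. It does not supply a measure for the non-enrolled unsuppressed patients or for the period after month 6.

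A reader might infer several stronger things that the document does not support:
- **That the clinic rate cannot show an effect.** Clinic size and u are named only as matching variables, without values. Under the assumptions above, whole-clinic power at N = 1,000 runs from 0.07 to 0.92. Attenuation is certain for any u below 100%; its severity is unknown.
- **That new initiators are pure dilution.** They are offered the guidance, and their partners may attend the sessions.
- **That the reading definitely falls 3 months after the intervention.** This needs clinic baseline to be the intervention start, which is not stated.
- **That a flat rate will be read as no effect, or that a change would mostly reflect who entered or left the clinic.** The plan proposes no such interpretation, and the document has no data on turnover.

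The alternative measure has limits too. A cohort closed at the start leaves out initiators and anyone who becomes unsuppressed later, and patients first reached late in the period would have little exposure by month 9.

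**Conclusion.** The concern holds as a matter of attenuation and fit, not of impossibility. The one viral measure that looks past the enrolled dyads and past month 6 is, on its natural reading, taken in a population different from the one in which effects are to be assessed. The direction follows from arithmetic; the size, 0.4 to 6 points for a 20-point gain, rests on the assumed range of u. A cohort unsuppressed at a fixed date does better at every u examined, and also when only enrolled patients gain. The timing point is conditional on the clinic baseline date.

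This is a low-cost improvement to an exploratory measure in a pilot. It does not make the clinic comparison causal: with one clinic per arm, clinic and intervention effects cannot be separated under either denominator.

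**What to change.** 1. Set one calendar date, the intervention start and the same in both clinics, as the clinic-level baseline, and state the denominator of the whole-clinic rate.
2. In addition to that rate, report for each clinic the percentage suppressed among patients who at that date had been on ART for at least 6 months and had a viral load of 400 cp/ml or more. Report it at month 12 and, where routine records allow, at month 9. State whether one high reading is enough or whether two within 12 months are needed, as for enrolment.
3. Add a line to the Statistical Analysis Plan that both figures are descriptive and exploratory, and that the whole-clinic rate is diluted context for the unsuppressed group.

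**Cost.** A change of wording, plus a larger request to the clinics, as counts or de-identified records, covering patients who are not enrolled. The plan already obtains the number unsuppressed per clinic for matching, but following that group forward goes beyond those counts and may need data-access approval.

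Separately, the protocol gives both 60 patients at 30 per clinic and 80 patients at 20 per clinic (80/20 = 4 clinics, not one pair). These must be reconciled; the calculations here use 30 per clinic and one clinic per arm.

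### Clinic-wide suppression rates at two dates in two clinics cannot separate the clinics' own trends from an intervention effect; repeating the seven-clinic count at 12 months would give a drift reference

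*Combined protocol and SAP*

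**What the plan says.** The clinic-wide outcome appears in one sentence of the Study Protocol, in the paragraph on assessments after the Intervention Pilot Test description: "We will obtain viral load suppression rates for the intervention and control clinic at baseline and 12-months post-baseline". No other dates and no other clinics are named for it.

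The Intervention Pilot Test paragraph places the study "in 1 matched-clinic pair (30 dyads/clinic) in Gaborone, Botswana". Allocation is by clinic: "Clinics will be randomly assigned to standard of care or a healthcare provider guidance and treatment partner training intervention". To choose the pair, the team starts from a wider pool: "We will obtain updated data on 7 satellite clinics in the Greater Gaborone area". It will then "match satellite clinics on number and type of staffing, number of patients total, and number of unsuppressed patients". All of these matching variables describe the present state of a clinic. None describes how its suppression rate has been moving.

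The Statistical Analysis Plan gives no method for the clinic-wide rates. Its logistic regression for suppression is confined to enrolled patients. It describes the analyses as exploratory, regards formal outcome tests as unjustified at this sample size, and does not claim adequate power.

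A later sentence of the Study Protocol conflicts with the single pair: "We will recruit 80 patients (20 per clinic; half men and half women) and their 80 treatment partners".

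**The concern.** The natural use of the four rates is to subtract the control clinic's change from the intervention clinic's change. A trend common to both clinics cancels in that subtraction. A trend peculiar to one clinic does not, and the plan provides no way to see it. There is no earlier date to show whether the two clinics were already diverging, and no further clinic to show how far a rate moves in 12 months without the programme.

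Matching on current staffing and counts does not balance trends. Randomising within one pair makes the assignment fair, but gives no measure of how large a chance difference in trend might be. Enlarging the clinics or cleaning up the denominator would not help either, because the missing information is at clinic level.

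At stake is the reading of the clinic-wide difference. Aim 2 seeks early signals of effect on suppression to inform a full trial. The SAP's caution concerns small numbers; it does not tell the reader that trend and effect are inseparable here.

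**Working it through.** The documents state no clinic-level rate, effect size or drift figure, so there is no figure of the plan's own to reproduce.

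**1. Degrees of freedom.** Inputs: 2 clinics (Intervention Pilot Test) and 2 dates (assessments paragraph).
- Values: 2 × 2 = 4.
- Parameters of a difference-in-change model: intercept, clinic, period, clinic × period = 4.
- Residual df: 4 − 4 = 0. The clinic × period term carries both the effect and any difference in trend, and no variance between clinics can be estimated.

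**2. How large a chance difference might be.** Assumptions, not from the documents: the SD τ of a clinic's own 12-month change is 1, 2 or 3 percentage points; changes are normal and independent between clinics; there is no true effect; 2 points is the apparent gain of interest. Sampling error of each rate is ignored.
- SD of the difference between two clinics = √2 × τ.
- P(difference ≥ 2) = 1 − Φ(2 / (√2 τ)).

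| τ (points) | SD of difference | P(apparent gain ≥ 2) |
|---|---|---|
| 1 | 1.4 | 0.079 |
| 2 | 2.8 | 0.240 |
| 3 | 4.2 | 0.319 |

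**3. Why more patients per clinic do not cure this.** Suppose someone attached a binomial-only standard error to the difference (the plan does not). With rate p and n patients per clinic per date:
- binomial-only SE = √(4p(1−p)/n);
- SE including drift = √(4p(1−p)/n + 2τ²);
- two-sided false-positive rate = 2[1 − Φ(1.96 × binomial SE / SE with drift)].

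Assume p = 0.90 and τ = 2 points. At n = 1000 the two SEs are 0.0190 and 0.0341, and the false-positive rate is 27.5%. It is 12.9% at n = 300 and 47.9% at n = 3000. A larger n makes the misreading more likely, not less.

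**4. What the other clinics would add.** Under the single-pair design:
- clinics not selected: 7 − 2 = 5; clinics without the programme: 5 + 1 control = 6;
- the SD of change is then estimable on 6 − 1 = 5 df;
- 95% limits for that SD, as multiples of the estimate s: √(5/χ²₀.₉₇₅) to √(5/χ²₀.₀₂₅) = 0.62 to 2.45;
- 95% prediction half-width for one further clinic's change: t₀.₉₇₅,₅ × √(1 + 1/6) × s = 2.78 s;
- chance that the intervention clinic ranks first of 7, if all seven changes are exchangeable: 1/7 = 0.143, against 1/2 with the control clinic alone.

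**5. Dependence on the clinic count.** The Intervention Pilot Test paragraph gives 60 / 30 = 2 clinics. The later recruitment sentence gives 80 / 20 = 4, which would leave 7 − 4 = 3 unselected. Steps 1 and 4 follow the first of these.

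**The case against.** The strongest reply is that this is an acknowledged pilot. The SAP calls the work exploratory, disclaims formal tests and power, and models suppression only in enrolled patients. The Study Protocol limits the assessment of effects to patients who are not suppressed. No test, interval or decision rule is attached to the clinic-wide rates. This stands, and it limits the point to how one descriptive comparison is read. A reader might infer that the flaw undermines the enrolled-patient analysis; that is a separate outcome and the point does not extend to it.

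Other stronger readings also fail:

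- **Earlier clinic rates are at hand.** The reference to updated data hints at an older data set, but its content and dates are not given. The 12 months of prior viral loads are individual eligibility checks. Earlier clinic-level rates may or may not be retrievable.
- **Follow-up on the five other clinics is already planned.** Only matching-time data are. Twelve-month counts would be a new request.
- **1/7 is a p-value.** Randomisation was only within the chosen pair, and by itself supports 1/2. The other clinics were passed over by the matching, so 1/7 rests on assumed exchangeability and is a descriptive reference. Pooling six clinics into one SD also assumes similar variance, although clinic size may differ.
- **The pilot loses a key planning figure for the full trial.** That would follow only if the full trial used the clinic-wide rate as its outcome, which the documents do not say. An SD on 5 df would in any case be rough.

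It is also fair to say that the drift values are wholly assumed. They show that drift could matter, not that it does.

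**Conclusion.** The point holds in a limited form. As planned, the clinic-wide difference in change has 0 residual df, so trend and effect are completely confounded and between-clinic variation in change cannot be estimated. This conclusion needs no assumption beyond the single pair and the two dates. The size of the problem is unknown: the 8%, 24% and 32% figures depend on assumed drift SDs of 1 to 3 points and an assumed 2-point threshold.

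The consequence is confined to an exploratory comparison for which the SAP specifies no analysis. The improvement is worth making because it is cheap: the counts that give a starting rate for every clinic are already to be collected. It would supply a reference for drift, not proof of effect. With one treated clinic, conventional significance is out of reach even after the change.

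**What to change.** 1. Reconcile the two recruitment statements (60 patients at 30 per clinic; 80 at 20 per clinic), so that the number of study clinics and of unselected clinics is fixed.
2. Repeat at 12 months the aggregate pull of total and unsuppressed patients planned at matching, for all 7 satellite clinics, using the same definition of unsuppressed and the same calendar dates in each clinic.
3. If records allow, take earlier rates for the same clinics, for example at −12 and −6 months, and show each clinic's series.
4. Add to the SAP that the clinic-wide rates are reported descriptively; that the intervention–control difference in change is shown against the spread of changes in the clinics without the programme; that a difference within that spread is not evidence of an effect; and that one treated clinic cannot give conventional significance. Label any rank statement as descriptive and dependent on exchangeable clinics.
5. If the further data cannot be obtained, keep at least the statement that trend and effect cannot be separated.

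The cost is an additional aggregate data request to the unselected clinics, some data work and a few sentences of text, with no patient contact. The clinic-level result will read as less definite.
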